7.4 Handling of Missing, Unused, and Spurious Data and Dropouts

Every effort will be undertaken to minimize missing data. In time-to-event outcomes, dropouts will be censored at the time of discontinuation, consistent with the Kaplan-Meier approach. Unless specified otherwise in each objective, no statistical techniques will be used to impute missing data. If a subject's data are missing for any reason, that subject will not be included in that portion of the analysis. The number of subjects included in each analysis will be reported so that the potential impact of missing data can be assessed.

In the case of partial dates, the general rule is as follows:

- If only the month and year are known, the event or assessment will be analyzed as if it occurred on the 15th of that month.
- If only the year is known, the event or assessment will be analyzed as if it occurred on June 30th of that year.

These resolutions of partial dates are subject to the restrictions that pre-procedure events and assessments must occur between the enrollment date and the procedure date, and post-procedure events and assessments must occur no earlier than the procedure date. If additional information about the partial dates might be known, for example, the event occurs after 15th of the month, then data may be analyzed as if it occurred on the 16th of the month.

7.5 Adjustments for Multiple Comparisons

There are no planned multiple comparisons expected and thus no multiplicity adjustments are planned for this study.

7.6 Demographic and Other Baseline Characteristics

Major baseline demographic and clinical variables will be summarized for the enrolled and implanted populations. All continuous variables will be summarized with means, standard deviations, medians, interquartile ranges, minimums, and maximums. Categorical variables will be summarized with frequencies and percentages.

7.7 Treatment Characteristics

Implant procedure data will be summarized for the implanted populations. All continuous variables will be summarized with means, standard deviations, medians, interquartile ranges, minimums, and maximums. Categorical variables will be summarized with frequencies and percentages.

Revision 7.0

Page 13 of 22

7.8 Interim Analyses

Interim analysis is planned when at least 200 patient-years of data are collected. However, there are no plans for early termination of the trial due to superiority or futility of the investigational therapy based on the interim results.

An interim analysis of the trial data is planned to evaluate the early safety profile of the Model 400 valve. The interim analysis may be included as supplementary information in a submission for CE Mark and may be used for regulatory submissions in other geographies.

7.8.1 Safety Objective

The safety objective is to evaluate the safety of the Model 400 valve with regard to valve-related adverse events and death.

7.8.1.1 Endpoints

Safety of the valve will be evaluated by the time-related incidence of valve-related adverse events with OPC. The following valve-related adverse events will be evaluated in this analysis: Thromboembolism, Thrombosis, Major Paravalvular leak, Endocarditis.

7.8.1.2 Hypothesis

The safety objective will be assessed by comparing a composite linearized adverse event rate from subjects implanted with the Model 400 valve to twice the composite linearized adverse event rate of valve-related Thromboembolism, Endocarditis, Major PVL and Thrombosis. The composite rate was developed using individual valve-related event rates from the Objective Performance Criteria (OPC) as defined by FDA Heart Valve Guidance 2010^{vi} and EN ISO 5840:2009ii From Table 1, twice the composite linearized adverse event rate of Thromboembolism, Endocarditis, Major PVL and Thrombosis is $2 \times (2.5 + 0.2 + 0.6 + 1.2) = 9\%$ per patient year.

The interim analysis hypothesis is to test that the true composite linearized adverse event rate of Thromboembolism, Endocarditis, Major PVL and Thrombosis for the Model 400 valve (P Model400) is equal to or greater than twice the composite linearized adverse event rate of commercially available tissue prosthesis valves.

The null (H₀) and alternative (H_A) hypotheses are written as follows:

Ho: P Model400 $\ge 9\%$ HA: P Model400 < 9%

Where P_Model400 is the composite linearized adverse event rate for the Model 400 valve.

7.8.1.3 Sample Size Methods and Assumption

7.8.1.3.1 Sample Size Methods and Assumptions

The objective will be evaluated with a fixed sample size group sequential design with one interim analysis at 200 patient-years and one possible second analysis at 400 patient-years.

Medtronic PERIGON Pivotal Trial Statistical Analysis Form Plan Medtronic Page 14 of 22 Revision 7.0

A fixed sample size group sequential design with O'Brien-Fleming boundaries for one interim analysis will be utilized. A fixed sample size design of 400 patient-years with one interim analysis at 200 patient-years achieves at least 90% power. The assumptions for sample size / power calculation:

- P Baseline (the baseline rate: observed in the literature) = 3.5%
- P Model400 (the assumed rate for Model 400) = 3.5%
- Type I error (α) =0.05 ٠
- One interim analysis at 200 patient-years •

7.8.1.3.2 **Rationale for Choice of Hypothesis**

The composite rate and hypothesis were chosen because it provides an overall evaluation of safety of the device by incorporating significant device-related events that are clinically relevant to evaluating a new bioprosthetic heart valve.

7.8.1.4 Data Collection and Analysis Method

There will be up to two analyses of this objective. The first analysis may occur when 200 patientyears of data are collected, and the second analysis may occur when 400 patient-years of data are collected. Spending function with boundaries similar to that for O'Brien-Fleming^{vii} will be used to control the Type I and Type II error probabilities. The table below illustrates the O'Brien-Fleming boundaries and the associated z-statistic and p-value for each analysis under an assumption that 200 patient-years of data are observed at the interim analysis. However, if the observed patient-years of data are different at the time of the interim analysis, the boundaries and p-values will be recalculated to reflect the appropriate percentage of the total sample size observed at the time of the interim analysis.

Analysis	Z-statistic	P-value
Interim	-2.3585, 0.0000	0.0092, 0.5000
400 patient-years	-1.6677	0.0477

Table 2: O'Brien-Fleming boundary at the interim and 400	patient-year analysis
--	-----------------------

*S-Plus 8.2/S+ SegTrial used with the O'Brien-Fleming Type I error spending function.

The above sample rate boundaries are also shown in Figure 1:

Since there may be up to two analyses, there are two thresholds for which the observed test statistic will be evaluated. Call this set of thresholds $Z_t = (Z_1, Z_2)$. Each of these thresholds will be a standard normal Z statistic evaluated at the nominal alpha level for the analysis. For example, in the table above, the nominal alpha level for the interim analysis is 0.0092 with an associated Z statistic of -2.3585. Thus, if the Z statistic is smaller than -2.3585, the null hypothesis may be rejected at the interim analysis. Similarly, if the null hypothesis cannot be rejected at the interim analysis, the null hypothesis may be rejected at the 400 patient-years analysis provided the Z statistic is smaller than -1.6677. To reject the null hypothesis demonstrates statistically that the Model 400 valve composite adverse event rate is less than 9%. This method preserves the Type I error rate at 5% since the conservative O'Brien-Fleming rules are utilized in setting the rejection thresholds Z_t .

- At the interim analysis (200 patient-years), if the data support the alternative hypothesis that the Model 400 valve composite rate is <9%, the results will be summarized and submitted as applicable as described in section 7.8. The 400 patient-year analysis will not be performed under this scenario.
- If the criteria are not met at the 200 patient-year interim analysis, the trial will continue to gather data to at least 400 patient-years and then summarize the data and submit as applicable as described in section 7.8.

In both scenarios, the trial conduct will not be altered, and the trial will not stop, but continue until at least 800 patient-years of data are collected.

Medtronic PERIGON Pivotal Trial Statistical Analysis Form Plan Revision 7.0 Page 16 of 22 Medtronic

Z test will be carried out to assess statistical significance, and the test statistic will be calculated as:

$$z = \frac{p - \pi_0}{\sqrt{\pi_0 / n}}$$

In the above expression π_0 =9% per patient-year, the Performance Goal, p is the late linearized rate of the composite events, which is calculated as number of late events divided by late patient-years, and n is late patient-years. The test is one-sided and the resulting p-value will be compared to the interim O'Brien-Fleming p-value.

Each component of the composite adverse event rate will also be summarized and described. Kaplan-Meier survival analyses will also be performed to summarize the adverse event data.

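### The interim test's flat 5% error claim is not a property of the stated rule: the boundaries assume a futility stop that is not applied, and the z test lets the exact error pass 5% in narrow ranges of follow-up

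*SAP*

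**What the plan says.** SAP 7.8 and protocol 7.2 plan a composite test of thromboembolism, endocarditis, major paravalvular leak and valve thrombosis against 9% per patient-year. There is one look at 200 patient-years and possibly a second at 400.

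- **Error level:** "Type I error (α) =0.05" (SAP 7.8.1.3.1).
- **Boundaries:** in SAP Table 2 and protocol Table 9 the interim row reads, after a minus sign, "2.3585, 0.0000", and the final value is −1.6677. The text uses only the two negative values and never says what Z = 0 does.
- **If the interim criteria are not met:** data are gathered to at least 400 patient-years and then summarized (SAP 7.8.1.4). Either way, "the trial conduct will not be altered, and the trial will not stop". SAP 7.8 also says that no early termination for futility is planned.
- **Test:** "Z test will be carried out to assess statistical significance", with z = (p − π₀)/√(π₀/n). Here π₀ is "9% per patient-year, the Performance Goal, p is the late linearized rate of the composite events", and n is late patient-years. "The test is one-sided and the resulting p-value will be compared to the interim O'Brien-Fleming p-value".
- **Claim:** "This method preserves the Type I error rate at 5" per cent, attributed to the conservatism of O'Brien-Fleming rules.

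**The concern.** A futility boundary uses up part of the chance of a false rejection: runs that cross it cannot be rejected later. The efficacy boundaries can then be set slightly looser. If the stop is counted in the calculation but not carried out, the looser boundaries remain and the error is no longer what was solved for.

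Separately, the test applies a normal approximation to counts expected to be about 18 and 36 under the null. With a discrete count, the real error depends on where the realised patient-years fall relative to the points at which the allowed number of events goes up by one.

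At stake are a stated operating characteristic and, at some totals, a pass or fail that turns on one event, in a test that feeds a CE Mark submission.

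**Working it through.** **Inputs (SAP 7.8.1.3.1 and 7.8.1.4).** One-sided α = 0.05; null rate 0.09 per patient-year; assumed rate 0.035; looks at 200 and 400 patient-years; boundaries −2.3585 and −1.6677, with Z = 0 listed at the interim.

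**Step 1: reproduce Table 2.** Take (Z₁, Z₂) as bivariate normal with correlation √(200/400) = 0.707 and the O'Brien-Fleming shape Z₁ = √2 × Z₂.

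- With a binding stop at Z₁ ≥ 0: α = P(Z₁ < −2.3585) + P(Z₁ < 0, Z₂ < −1.6677) − P(Z₁ < −2.3585, Z₂ < −1.6677) = 0.0092 + 0.0466 − 0.0057, which is 0.0500 before rounding of the terms. Solving for 0.05 returns exactly −2.3585 / −1.6677.
- Without the stop, the middle term becomes P(Z₂ < −1.6677) = 0.0477: α = 0.0092 + 0.0477 − 0.0057, which is 0.0511 before rounding.
- Solving for 0.05 without the stop gives −2.3730 / −1.6780 (p 0.0088 / 0.0467). Lan-DeMets O'Brien-Fleming spending without futility gives −2.538 / −1.662. Neither matches the table.

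So the tabulated pair belongs to a design with a binding stop at zero.

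**Step 2: exact error of the z rule, no futility stop.** Let c₁ and c₂ be the largest counts that pass each look, and X₁ and X₂ the Poisson counts in the first and second segments. Then α = P(X₁ ≤ c₁) + Σ P(X₁ = i) P(X₂ ≤ c₂ − i) for i = c₁ + 1 to c₂, at rate 0.09.

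| Late patient-years (interim / final) | c₁ / c₂ | Exact α |
|---|---|---|
| 200 / 400 | 7 / 25 | 3.57% |
| 200 / 400.1 | 7 / 26 | 5.20% |
| 200.5 / 400.5 | 8 / 26 | 5.32% |
| 201 / 401 | 8 / 26 | 5.24% |
| 200 / 402 | 7 / 26 | 4.93% |
| 200 / 405 | 7 / 26 | 4.52% |
| 200 / 410 | 7 / 26 | 3.91% |

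The step is visible in one number. At 400.0, 26 events give z = (26 − 36)/√36 = −1.6667, which misses −1.6677. At 400.1 they give (26 − 36.009)/√36.009 = −1.6680 and pass. With the interim at 200, α is above 5% only from 400.08 to 401.49, and again briefly after each later step (for example 412.97 to 414.40). With the interim just above 200.1, the first window runs to 402.84. Over totals uniform on 200–220 and 400–430 with Table 2 unchanged, about 21% exceed 5%; the maximum is about 5.4%.

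**Step 3: which defect causes the excess?** At 200.5/400.5 the exact error is 5.32% without the futility stop and 5.28% with it. At 400.08 with the interim at 200, it is 5.20% without and 5.10% with. Correcting only the boundaries and keeping the z test still gives 5.07% at 200/401. The excess above 5% is therefore mainly a matter of the approximation and the discrete count.

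**Step 4: the z rule also errs the other way.** At exactly 200, 8 events give z = (8 − 18)/√18 = −2.3570 and narrowly fail, although P(X ≤ 8 | 18) = 0.0071 is below 0.0088. At the assumed 3.5% rate (7 events expected), the chance of passing the interim is 60% with cutoff 7 and 73% with cutoff 8.

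**Step 5: exact p-values at 0.0088 / 0.0467.** The cutoffs become 8 / 25 at 200.5/400.5, with error 3.7%. Just above 400 the error is about 3.7–3.8%. Over 200–220 / 400–430 the maximum is about 5.02–5.05%, with about 0.1% of totals above 5%. Power at 3.5% is about 99.7%.

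**The case against.** The strongest reply is that, at the planned looks, the stated rule is conservative: 3.57% exact, with no futility stop. This stands, and it rules out a reading that a reader might take from Step 1, namely that 5% holds only if the trial stops at Z = 0. That is true of the normal-theory calculation, not of the actual test at 200 and 400.

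A second tempting reading is that the missing stop pushes the error above 5% as soon as follow-up passes 400. Neither half is supported. The stop accounts for 0.04 points at 200.5/400.5, and the excess disappears by about 402–403 until the next step.

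A third point concerns the count of patient-years. The looks are triggered by patient-years of data, but n in the formula is late patient-years. If the trigger counts total patient-years, n will be below 400 at the second look, by up to about 30 days per implant. The plan does not settle this. It moves the analysis to another place on the same sawtooth: with the interim held at 200 and n from 340 to 400, the exact error ranges from 3.5% to 5.2%.

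It is also fair to say that a normal approximation with 18 and 36 expected events is common practice, that protocol 7.2 calls the interim analysis supplementary, and that the main event-by-event tests in SAP 7.9.1 do not use these boundaries. At the assumed rate about 0.035 × 400 = 14 events are expected, far from the disputed 25 or 26. All of this limits the size of the problem. None of it makes the unqualified 5% statement correct, or explains a tabulated boundary that the text does not use.

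**Conclusion.** The point holds as two separate, small defects. The boundaries were solved for a futility stop that the plan does not carry out (normal-theory error 5.11% instead of 5.00%). The z test has an exact error that varies with the realised patient-years, from well below 5% to about 5.4%.

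The windows above 5% are narrow, but one of them starts just above 400, where a cutoff date set on the first qualifying day would tend to fall. SAP 7.2.2.1 uses such a date for the PMA report at 800 patient-years and says that the CE mark report is handled similarly. If 350 to 550 subjects are under follow-up (an assumption), one day adds about 350/365 = 1.0 to 550/365 = 1.5 patient-years. That overshoot lies largely inside the first window.

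The figures assume that n at the looks is the late patient-years shown, that the composite count is Poisson, and that Table 2 is used unchanged. The plan recalculates boundaries if the interim total differs, but does not say whether Z = 0 is kept. The documents do not support a conclusion that the primary safety tests are affected or that power is at risk.

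**What to change.** In SAP Table 2 and protocol Table 9:

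1. Delete the Z = 0 entry or label it non-binding.
2. Replace the boundaries with −2.3730 / −1.6780 (one-sided p 0.0088 / 0.0467), and state that any recalculation at the observed information fraction is done without futility.
3. Replace the z statistic with the exact p-value P(X ≤ observed | 0.09 × late patient-years), compared with the threshold for that look. SAP 6.1 already uses Poisson probabilities for the main sample size.
4. State whether 200 and 400 count total or late patient-years.

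Steps 2 and 3 belong together, since new boundaries on the z scale still give 5.07% at 200/401. They are a large improvement but not a strict bound. If a strict bound is wanted, choose the final event cutoff so that the exact two-look Poisson error at the realised late patient-years is at most 5%. Otherwise, say that the error is approximately 5%.

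The cost is a few table entries, one formula and one sentence. Power at the assumed 3.5% stays near 99.7%, against the stated minimum of 90%.

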7.8.2 Effectiveness Objective

The effectiveness objective is to confirm the effectiveness of the Model 400 valve regarding the NYHA Functional Classification and hemodynamic performance.

7.8.2.1 Endpoints

The effectiveness endpoints are:

- NYHA Functional Classification (at discharge or within 30 days, 3-6 months, 1 year and annually thereafter through 5 years)
- Hemodynamic Performance (at discharge or within 30 days, 3-6 months, 1 year and annually thereafter through 5 years) including
 - o effective orifice area (EOA)
 - effective orifice area index (EOAI)
 - peak pressure gradient
 - mean pressure gradient
 - valvular regurgitation
 - o performance index
 - o cardiac output
 - o cardiac index

7.8.2.2 Hypothesis

No formal hypothesis will be evaluated for this objective. Control articles based on current literature of previously approved heart valves will be selected. Data from the control articles will be provided so as to inform the reader of the current state of heart valve technology, as expressed by articles in quality peer-reviewed journals, and to allow for evaluation of the Model 400 data.

7.8.2.3 Sample Size Methods and Assumptions

Sample size calculations were not performed for the effectiveness objective. Sample size for the interim analysis was based on the safety objective.

Revision 7.0

Page 17 of 22

Medtronic

7.8.2.4 Data Collection and Analysis Methods

NYHA functional classification and echocardiographic hemodynamic data will be summarized using descriptive statistics for continuous variables and frequency tables for discrete variables.

For NYHA, a frequency table will be presented for each visit interval to show how many subjects fall into each of the four categories of NYHA functional classification. For each subject with paired data, the number of classes changed from baseline will be calculated at discharge (or 30 days), 3-6 months, 1 year and annually thereafter through 5 years and summarized into categories as Improved, No Change and Worsened.

All echocardiograms will be analyzed by an echo core lab which will determine the values for the Hemodynamic Performance endpoints. Valvular regurgitation will be summarized with a frequency table for each visit interval and the other Hemodynamic Performance endpoints will be summarized as with continuous data. For each subject with paired data, the change from baseline may also be calculated at discharge (or 30 days), 3-6 months, 1 year and annually thereafter through 5 years. These data will be summarized by valve size.

Control articles based on current literature of previously approved heart valves will be selected. Effectiveness data from the control articles will be provided so as to inform the reader of the current state of heart valve technology, as expressed by articles in quality peer-reviewed journals, to allow for evaluation of the Model 400 valve effectiveness data.

7.9 Evaluation of Objectives

7.9.1 Safety Objective

The safety objective is to evaluate the safety of the Model 400 valve with regard to valve-related adverse events and death.

7.9.1.1 Endpoints

Safety of the valve will be evaluated by the time-related incidence of valve-related adverse events and death. The following valve-related adverse events will be evaluated in this trial: Thromboembolism, Thrombosis, Hemorrhage, Paravalvular leak (PVL), Endocarditis, Hemolysis, Structural valve deterioration, Non-structural dysfunction, Reintervention, Explant, and Death.

7.9.1.2 Hypothesis

The safety objective will be assessed by comparing linearized valve-related adverse event rates from subjects implanted with the Model 400 valve to acceptable linearized valve-related adverse event rates following valve replacement as defined by FDA in the Heart Valve Guidance 2010ⁱ and EN ISO 5840:2009ⁱⁱ as Objective Performance Criteria (OPC). The OPC for tissue valves (based on the linearized rate) are presented in Table 1.

The trial is designed to test the hypothesis that the true linearized adverse event rate for the Model 400 valve ($R_{Model400}$) is equal to or greater than twice the acceptable rate of commercially available tissue prosthetic valves (R_{OPC}). The null (H_0) and alternative (H_A) hypotheses are written as follows.

 $H_0: R_{Model400} \ge 2 X R_{OPC}$

 $H_A: R_{Model400} < 2 X R_{OPC}$

This document is electronically controlled Medtronic Business Restricted 056-F286, Statistical Analysis Plan Template CONFIDENTIAL Rev C

Medtronic PERIGON Pivotal Trial Statistical Analysis		Form
Revision 7.0	Page 18 of 22	Medtronic

Where $R_{Model400}$ is the linearized adverse event rate for the Model 400 valve and R_{OPC} is the acceptable rate of commercially available tissue prosthetic valves. To reject the null hypothesis demonstrates statistically that the rate for the Model 400 valve is less than two times the acceptable rate.

7.9.1.3 Data Collection and Analysis Methods

7.9.1.3.1 Data Collection and Analysis

Adverse device effects and outcomes will be identified and reported by the Investigator at all visits. All deaths and endpoint related adverse events will be reviewed by the CEC.

Early postoperative events are defined as those occurring on or before 30 days post-operative. Late postoperative events are those occurring after 30 days post-operative.

Early rates of adverse events will be calculated as the number of early adverse events divided by the total number of subjects, expressed as a percentage.

The late events rates will be calculated using the linearized event rate methodology. That is, the rate will be the number of late events divided by the late post-operative patient-years. For those adverse events with OPC available, the linearized rates and their associated one-sided upper 95% confidence bounds will be compared to the Objective Performance Criteria (OPC) to show that they are within acceptable limits. Formally, the method introduced by Cox^{iv} which gives the relatively most accurate results^v will be used:

χ .95,2 n_e +1/2Y_T

where ne is the number of late events and YT is the late post-operative patient-years. If there is 0 events, the one-sided upper 95% confidence bound will be 0.

Kaplan-Meier survival analyses will also be performed to summarize valve-related adverse events and death. The Kaplan-Meier rate and the corresponding 95% confidence interval will be presented for each visit interval. In addition, number of subjects at risk, number of events, number of censored subjects and the Kaplan-Meier survival curve or event curve will also be displayed.

In addition, control articles based on current literature of previously approved heart valves will be selected. Adverse event data from the control articles will be provided so as to inform the reader of the current state of heart valve technology, as expressed by articles in quality peer-reviewed journals, and allow additional evaluation of the Model 400 adverse event data.

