7.1.1.3 Sample Size

Sample size estimation is based on the methods of Grunkemeier²⁴. The amount of data required to test the null hypothesis using the smallest acceptable adverse event rate of 1.2% per patient-year (excluding Valve Thrombosis, Major Hemorrhage and Major PVL) is 800 patient-years. This estimation assumes a 95% confidence level, a power of 0.80, and an annual attrition rate of 5%. If all subjects are enrolled within a one year time frame, and followed for one year postoperatively, then a total of 556 implants are required. Accounting for potential variability in attrition and enrollment rate, a sample size of 650 was originally approved in protocol revisions 1B through 1D. With version 1E of the investigational protocol, the sample size has been increased to 1300. While the increased sample size adds exposure of the investigational device to a larger cohort of patients, the sample size is within acceptable limits based on the following justification:

- The current risk and benefit analysis suggests that the benefits of surgical aortic valve replacement far outweigh the risks associated with implant of an aortic bioprosthesis. Given the relatively low expected incidence of late valve-related adverse events and the assumed linearized occurrence of such events as detailed in the published OPC data from the FDA Heart Valve Guidance 2010 and ISO5840:2009, the increased risk to the overall population of subjects requiring SAVR is minimal.
- Due to the linearized OPC model utilized in the evaluation of the primary safety endpoints, an increased sample size will allow for a more rapid evaluation of the primary safety endpoints through faster accumulation of valve-years.
- A similar sample size has been used by both Medtronic and other industry sponsors in the evaluation of other tissue aortic valves that have a similar design, the same intended use, and the same primary safety endpoints as the PERIGON trial. Notably, the pivotal trial for the Medtronic Mosaic™ valve utilized a cohort of 1252 subjects for evaluation of the primary safety endpoints which were compared to the same published OPC. Likewise, the most recently approved tissue aortic valve, Trifecta™, which is manufactured by St. Jude Medical, utilized a cohort of 1014 subjects for evaluation of the primary safety endpoints compared to the same published OPC. Therefore, there is historical precedent that a cohort similar to that of the PERIGON trial is justified.

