7.1.1.4 Analysis Methods

Primary endpoint analyses for regulatory approval will be done on consecutive subjects, and according to the requirements of the guidance documents:

- ISO5840:2009: for regulatory submissions in geographies adhering to the ISO5840:2009 standards (minimum of 150 subjects with 1 year follow up and 400 patient years)
- FDA Heart Valve Guidance 2010 for US FDA PMA (minimum of 300 subjects with 1 year follow up and 800 patient years).

Early rates of adverse events will be calculated as the number of early adverse events divided by the total number of subjects, expressed as a percentage. Early events are events occurring on or before 30 days post-operative.

Linearized rates will be calculated as the number of late events divided by the cumulative late post-operative patient-years, expressed as a percentage. Late events are events occurring after 30 days post-operative. For those adverse events with OPC available, the linearized rates and their associated one-sided upper 95% confidence bounds will be compared to 2 x the OPC rate to show that they are within acceptable limits.

Kaplan-Meier survival analyses will also be performed to summarize the adverse event data.

In addition, control articles based on current literature of previously approved heart valves will be selected. Adverse event data from the control articles will be provided so as to inform the reader of the current state of heart valve technology, as expressed by articles in quality peer-reviewed journals, and allow additional evaluation of the Model 400 adverse event data.

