6.1 Sample Size Methods and Assumptions

Adverse Event	Linearized Rate
	(% per Patient-year)
Thromboembolism	2.5
Valve Thrombosis	0.2

Table 1: OPC for Tissue Prosthetic Heart Valves

Medtronic PERIGON Pivotal Trial Statistical Analysis Plan		Form
Revision 7.0	Page 8 of 22	Medtronic
All Hemorrhage	1.4	
All Paravalvular Leak Major Paravalvular Leak	1.2 0.6	
Endocarditis	1.2	

The safety objective will be assessed by comparing linearized valve-related adverse event rates from subjects implanted with the Model 400 valve to acceptable linearized valve-related adverse event rates following valve replacement as defined by FDA in the Heart Valve Guidance 2010ⁱ and EN ISO 5840:2009ⁱⁱ as Objective Performance Criteria (OPC). The OPC for tissue valves (based on the linearized rate) are presented in Table 1.

Sample size estimation is based on the methods of Grunkemeier^{III}. The following are assumptions for the sample size estimate:

One-sided alpha = 0.05 Power = $1 - \beta = 80\%$ $2XR_{OPC} = 2.4\%$ $R_{Model400} = 1.2\%$

In the above expressions, $2XR_{OPC}$ and $R_{Model400}$ denote the Performance Goal (null hypothesis proportion) and true proportion, respectively.

If the endpoint event has a constant risk of $R_{_OPC}$ per patient-year, then the distribution of the number of endpoint events occurring during a fixed time of T patient-years is a random variable E with Poisson distribution of mean $\lambda = R_{_OPC} \times T$. Thus, the probability of observing n or fewer events during T patient-years is:

$$P_{\lambda}(E \le n) = \sum_{k=0}^{n} e^{-\lambda} \frac{\lambda^k}{k!}$$

To reject the null hypothesis of $R_{Model400} \ge 2 X R_{OPC}$, the number of events E occurring during T patientyears is less than or equal to the critical value of n_{cv} . The critical value of n_{cv} is determined by the selected Type I (α) and Type II (β) levels. That is:

$$\begin{cases} P_{2\lambda}(E \le n_{c\nu}) \le \alpha \\ P_{\lambda}(E \le n_{c\nu}) \ge 1 - \beta \end{cases}$$

Thus the amount of data required to test the null hypothesis using the acceptable adverse event rate of 1.2% per patient-year is approximately 800 patient-years using the Poisson distribution, an alpha level of 5% and at least 80% power.

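### The SAP's primary safety comparison sets the upper bound against 1 x OPC, whereas its own hypothesis, its sample size and the protocol use 2 x OPC

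*SAP*

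**What the plan says.** Two sentences describe the same step, and they differ in the limit.

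- Protocol 7.1.1.4 (Analysis Methods), for events that have an OPC: "one-sided upper 95% confidence bounds will be compared to 2 x the OPC rate to show that they are within acceptable limits".
- SAP 7.9.1.3.1 (Data Collection and Analysis), for the same events: "one-sided upper 95% confidence bounds will be compared to the Objective Performance Criteria (OPC) to show that they are within acceptable limits".

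The rest of the SAP sides with the protocol. In SAP 7.9.1.2 the null hypothesis is a rate at or above 2 x OPC, and rejecting it "demonstrates statistically that the rate for the Model 400 valve is less than two times the acceptable rate". SAP 6.1 lists the OPC in Table 1 at the 1 x rates (1.2% for endocarditis and for all paravalvular leak). It then sets the performance goal separately, at 2 x 1.2% = 2.4%, against a true rate of 1.2%. Protocol 7.1.1.2 states the same 2 x hypothesis. SAP 7.11 says that the SAP agrees with the protocol and lists no change to this limit.

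**The concern.** The term OPC in SAP 7.9.1.3.1 cannot be read as already including the factor 2, because Table 1 fixes it at the 1 x rates and the SAP writes the factor out wherever it means the doubled rate. The sentence that carries out the test therefore contradicts the hypothesis it is meant to test.

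This limit decides the primary safety objective. Under the literal wording the stated 80% power does not apply, and a valve performing exactly at the acceptable rate would nearly always miss the limit. The SAP governs the PMA, CE mark and final reports and the main manuscript (SAP 7.2.1), and hypothesis-tested endpoints are to be independently validated (SAP section 8). A programmer working from 7.9.1.3.1 and a validator working from 7.9.1.2 would code different limits. If that were settled only after the counts were known, choosing the more lenient limit would be open to challenge.

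**Working it through.** **Inputs**
- "One-sided alpha = 0.05" (SAP 6.1); power of at least 80% (SAP 6.1).
- Sizing rate: true rate 1.2%, null rate 2.4% per patient-year (SAP 6.1).
- Exposure: "using the acceptable adverse event rate of 1.2% per patient-year is approximately 800 patient-years" (SAP 6.1).
- OPC rates: SAP Table 1 and protocol Table 8 (major hemorrhage, 0.9%, taken from the latter).
- Upper bound (SAP 7.9.1.3.1): the Cox approximation, read as χ²(0.95; 2n + 1) / (2Y), with n late events and Y late patient-years. The printed formula is partly garbled; this is the reading used here.

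**Step 1. Reproduce the plan's figure.** The SAP requires a critical count c with P(E ≤ c | 0.024T) ≤ 0.05 and P(E ≤ c | 0.012T) ≥ 0.80, E being Poisson. The smallest T that works is 811 patient-years with c = 12: type I error 0.0495, power 0.816. This agrees with about 800, so the trial was sized on 2 x OPC.

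**Step 2. Find the largest passing count at Y = 800 for a 1.2% event.**

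| Late events | Upper bound, % per patient-year |
|---|---|
| 4 | 1.057 |
| 5 | 1.230 |
| 12 | 2.353 |
| 13 | 2.507 |

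Against 1.2% (1 x) at most 4 events pass. Against 2.4% (2 x) at most 12 pass.

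**Step 3. Probability of passing when the true rate equals the OPC.** The expected count is 0.012 × 800 = 9.6.
- 1 x OPC: P(E ≤ 4 | 9.6) = 3.8%.
- 2 x OPC: P(E ≤ 12 | 9.6) = 82.8%.

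With 5 to 12 events the two readings give opposite answers. The probability of that is 82.8% − 3.8% = 79.0%.

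**Step 4. All OPC events, one at a time, same method, Y = 800.**

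| Event | OPC, % | Expected count | Max events, 1 x / 2 x | Pass, 1 x | Pass, 2 x |
|---|---|---|---|---|---|
| Thromboembolism | 2.5 | 20.0 | 12 / 29 | 3.9% | 97.8% |
| All hemorrhage | 1.4 | 11.2 | 6 / 14 | 7.1% | 83.9% |
| Endocarditis; all PVL | 1.2 | 9.6 | 4 / 12 | 3.8% | 82.8% |
| Major hemorrhage | 0.9 | 7.2 | 3 / 8 | 7.2% | 70.3% |
| Major PVL | 0.6 | 4.8 | 1 / 4 | 4.8% | 47.6% |
| Valve thrombosis | 0.2 | 1.6 | 0 / 0 | 20.2% | 20.2% |

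Valve thrombosis is a special case. By the formula, zero events gives a bound of 0.240%, already above 0.2%. The SAP separately sets the bound to 0 when there are no events, so zero events passes under either limit, and the limit makes no difference.

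**Step 5. A valve better than the OPC.** At half the rate (0.6%, expected count 4.8), a 1.2% event passes against 1 x OPC with probability P(E ≤ 4 | 4.8) = 47.6%.

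**Step 6. Sensitivity to exposure.** SAP 7.2.2.1 cuts the PMA data at 800 patient-years collected, while the bound uses time after day 30 only. With an assumed 740 late patient-years (expected count 8.88; at most 4 or 11 events), the 1.2% events pass 5.9% of the time against 1 x and 81.4% against 2 x.

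**The case against.** The best counter-argument is that this is a slip and not a changed test. SAP 7.9.1.3.1 says only that bounds are compared with the OPC; it does not say when the null hypothesis is rejected. The rejection criterion appears in SAP 6.1 and 7.9.1.2, both times at 2 x OPC, so a careful analyst would use 2 x. That is probably right about the intent, and it means a wrong failure follows only if the sentence is applied literally. It does not remove the contradiction: this is the only place where the SAP says what the confidence bound is compared with, and the limit there is wrong.

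Four narrower points also stand.

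- A pass rate near 5% is what any test gives when the true rate sits at its limit, whatever the sample size. The 3.8% shows that the hypothesis has been swapped; it is not a further loss of power.
- The contrast of about 4% with about 80% belongs to the 1.2% events that sized the trial. Major hemorrhage, major PVL and valve thrombosis fall short of 80% even at 2 x OPC, and SAP 6.2 explains that they were left out of the sizing.
- A 1 x limit is stricter. It cannot pass a valve that 2 x would fail, so false acceptance does not rise.
- This SAP revision follows protocol version 1F (March 2019), after the 2017 approvals of the 19 to 27 mm sizes. Its main remaining use is the final report, with more follow-up. At an assumed 3,000 late patient-years, a 1.2% event at half the OPC would pass 1 x OPC 97% of the time, but one at the OPC would still pass only about 5% of the time.

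**Conclusion.** The concern holds: SAP 7.9.1.3.1 is wrong as written. It gives 1 x OPC as the limit for the primary safety comparison, against 2 x OPC in SAP 6.1, SAP 7.9.1.2 and protocol 7.1.1.2 and 7.1.1.4. At 800 late patient-years, for a valve exactly at the OPC, the literal rule cuts the chance of passing from 82.8% to 3.8% for endocarditis and all PVL, from 97.8% to 3.9% for thromboembolism, and from 83.9% to 7.1% for all hemorrhage.

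These figures assume Poisson counts at a constant rate, each event type considered alone, and the Cox bound as read above. The contrast is much the same at 740 late patient-years. The error runs towards wrongly failing an acceptable valve, never towards wrongly passing a poor one.

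**What to change.** In SAP 7.9.1.3.1, state that the linearized rates and their one-sided upper 95% bounds are compared with 2 x the OPC rate, as protocol 7.1.1.4 does. It would help to add that the null hypothesis of SAP 7.9.1.2 is rejected for an event type when its bound lies below that limit. If any report has already been produced under this SAP, it should say which limit was applied.

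The cost is a few words in an SAP revision. Data collection, sample size and the protocol stay as they are.
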